SECONDARY: Microbial translocation [Primarily, Lipopolysaccharide binding protein (LBP)], zinc level, oxidative markers, safety measures (% subjects with >Grade 2 adverse events possibly or probably to study drugs), lipid levels, insulin resistance (HOMA-IR), endoPAT, and blood pressure.

Design and Outcomes:

This is a pilot open labeled randomized double arm study, studying the efficacy and safety of Zinc therapy on cardiovascular outcomes in ≥ 18 years old HIV-infected patients, on stable ART (for at least 12 weeks) and with zinc levels ≤ 0.75 mg/L in the last 60 days.

Subjects will be evaluated and data will be collected according to the following schedule:

Evaluation (Weeks)	Screen	Entry*	Wk 4	Wk 10	W 16 or premature study discontinuation
Written consent form	X				
Inclusion/exclusion	X				
Family history of CVD/diabetes/HTN		X			
CVD Risk Score		X			X
Targeted physical exam/weight/blood pressure	X	X	X	X	X
Compliance assessment/safety monitoring			X	X	X
Smoking, illicit drugs and alcohol status		X			X
Dietary logs and Activity status		X			X
Height	X				
Hematology/chemistries	X	X	X	X	X
Urine β -HCG (women)	X	X	X	X	X
Fasting lipoprotein profile		X			X
Fasting insulin, glucose, HOMA-IR		X			X
Plasma inflammation markers		X			X
Microbial translocation (IFAB, LBP)		X			X
Oxidative markers		X			X
Zinc levels	X	X			X
Calcium Score		X			
DEXA		X			
Endothelial function		X			X
Resting Energy Expenditure (REE)		X			X
Stored fasting plasma, serum, urine and stool ***	X	X	X	X	X

Intervention and Duration:

The duration of the study will be 16 weeks. Patients will be given zinc gluconate capsules at a dose of 45 mg, or 90 mg, elemental zinc daily for 16 weeks. No additional follow up will occur after 16 weeks.

Sample size and population:

The total sample size is 50 patients, 25 patients will be randomized to one (45 mg) capsules and 25 patients will receive two 45 mg capsules (or 90 mg).

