pharmacy. Only site pharmacists can access the randomization schedule at the time of the intervention assignment.

Blinding:

Patients will be unblinded to treatment allocation (1 versus 2 zinc gluconate capsules). The research nurse, responsible for providing the patient with zinc gluconate capsules will also be unblinded to treatment assignment. They will provide the patient with the capsules (1 or 2 capsules) and assess patient's adherence to the pills. Patient's treatment as well as adherence to pills (pills count) will be collected by the research nurse and kept in a locked electronic data sheet, only they have access to. Only the percent adherence to treatment (a percentage) will be shared with the rest of research team and entered in the shared electronic database.

The research assistant as well as the principle investigator will remain blinded to treatment assignment. The research assistant will be responsible to prepare DSMP reports with the principal investigator and will include enrollment and dropout rates, protocol deviations, subjects symptoms, review of clinical, laboratory results and percent adherence to treatment, while remaining blinded to treatment allocation.

The principle investigator, as well as the DSMP board will remain blinded throughout the conduct of the clinical trial unless unblinding is warranted to optimize management of an adverse event or for other safety reasons. In these specific circumstances, the research nurse will be responsible for breaking the blind to the principal investigator. This will occur in a private location to ensure the rest of the team remains blinded.

All statistical analyses will also be done in a blinded fashion. Data will be exported to the statistician as arm A versus arm B by the research nurse to preserve blinding. For analyzing adherence, they will also only have access to the percent as opposed to pill counts the research nurse uses to calculate this.

TIMING OF EVALUATIONS

Screening

All screening evaluations to determine eligibility must be completed within 30 days prior to study entry.

Entry

Evaluations must occur within 30 days after screening evaluations. If subject shows up ill with any acute symptom, the visit will be postponed until all symptoms resolved for at least 7 days.

On-Study Evaluations

Study visits must be scheduled on the weeks indicated in the schedule of events +/- 14 days.

Premature study discontinuation

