As the transmission of HIV and other blood-borne pathogens can occur through contact with contaminated needles, blood, and blood products, appropriate blood and secretion precautions will be employed by all personnel in the drawing of blood and shipping and handling of all specimens for this study, as currently recommended by the Centers for Disease Control and Prevention and the National Institutes of Health.

All infectious specimens will be packaged and sent in accordance with requirements mandated by the International Air Transport Association Dangerous Goods Regulations- Packing Instruction 602.

DATA SAFETY AND MONITORING PLAN

This is a pilot study that will serve to collect preliminary data on the anti-inflammatory effects of zinc in HIV. However, an independent data and safety monitoring board will be established to include an independent HIV expert, a statistician, and a community advocate. The DSMB will meet every 6 months (or earlier as needed) to review safety data and adverse events. The DSMB will function to: review and approve plans for data and safety monitoring for this trial; to review data on a timely basis and to ensure proper conduct and progress of study; to review credentials of investigator and project staff; to make recommendations to project investigator and staff regarding issues of concern; to address adverse events. The DSMB will meet twice a year in Cleveland, Ohio or by phone conferences to review study protocols progress, and safety data. Meetings will be held in an open format, except if privileged data are discussed. At the time of the continuing review, the DSMB report will be prepared by [name] and her staff and will include enrollment and dropout rates, protocol deviations, subjects symptoms, review of clinical and laboratory results.

The DSMB will review interim data to detect evidence of adverse events to determine if the trial should continue as originally designed, should be changed or even stopped based on the data. The DSMB will evaluate the progress of the trial, including periodic assessments of the recruitment goals, protocol adherence, accrual and retention of participants. The DSMB will protect confidentiality of the study subjects.

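### Routine safety board reports, written by blinded staff for a blinded board, contain no by-arm table and so cannot show whether adverse events cluster at one dose

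*Combined protocol and SAP*

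**What the plan says.** **Design.** Under Sample size and population, "25 patients will be randomized to one (45 mg) capsules and 25 patients will receive two 45 mg capsules (or 90 mg"). There is no placebo arm, so dose is the only randomised contrast.

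**Who writes the board's reports.** The Blinding section states: "The research assistant as well as the principle investigator will remain blinded to treatment assignment". It then says: "The research assistant will be responsible to prepare DSMP reports with the principal investigator", and adds that this is done without knowledge of allocation. Treatment and pill-count data sit in a file open only to the research nurse, and the pharmacy holds the randomisation schedule.

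**Who reads them.** The principal investigator, "as well as the DSMP board will remain blinded throughout the conduct of the clinical trial", with an exception that follows at once: "unless unblinding is warranted to optimize management of an adverse event or for other safety reasons". In those cases "the research nurse will be responsible for breaking the blind to the principal investigator". I take the board named in the Blinding section to be the DSMB of the Data Safety and Monitoring Plan.

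**What they contain.** Both sections list enrolment, dropout, deviations, symptoms, and clinical and laboratory results. The Blinding section adds percent adherence. Neither mentions a breakdown by arm. Masked coding appears only for the statistical analyses: "Data will be exported to the statistician as arm A versus arm B by the research nurse to preserve blinding".

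**What the board must do.** Under the Data Safety and Monitoring Plan it reviews interim data on adverse events "to determine if the trial should continue as originally designed, should be changed or even stopped based on the data".

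**The concern.** The board is asked to judge the safety of a two-dose trial, yet nothing in its routine reports tells it which events belong to the same arm. The named authors could not supply that split if they wished to, because they have no access to allocation. Safety and tolerability is a stated secondary objective, and the Risks section itself links copper deficiency and related anaemia to higher doses and long use. A toxicity related to dose is therefore a pattern the board would want to recognise, and an uncoded report cannot display it.

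The exception for safety unblinding does not close the gap. Someone must first become concerned, and the reports meant to raise that concern lack the relevant split. No trigger is given, and the disclosure described goes to the principal investigator, with no stated route to the board.

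**Working it through.** The documents give no expected toxicity rate, stopping boundary or safety power, so there is no figure of the plan's to reproduce. **All toxicity rates below are assumptions.** The planned arm size of 25 per dose comes from Sample size and population.

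**1. What a pooled summary shows.** Pooled rate = (25 × p₁ + 25 × p₂) / 50 = (p₁ + p₂) / 2. If the event occurs at one dose only, the pooled rate is half the true rate:

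- 12% appears as 6%
- 20% appears as 10%
- 32% appears as 16%
- 40% appears as 20%

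With a background on the other dose, the pooled rate is the mean of the two: 10% and 30% give 20%.

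**2. What the split adds for the same total.** Exact 95% intervals and two-sided Fisher tests:

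- 5/50 (10%, 3.3% to 21.8%) could be 0/25 against 5/25 (20%, 6.8% to 40.7%), p = 0.050.
- 8/50 (16%) could be 0/25 against 8/25 (32%), p = 0.004, or 4/25 against 4/25, p = 1. An uncoded report reads the same in both cases.

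**3. How much detection improves.** Suppose an assumed background of 10%, with one dose truly higher. Compare two flags with similar false-flag rates when both arms are at background:

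- Pooled flag at 9 or more of 50: P(Bin(50, 0.10) ≥ 9) = 5.8%.
- By-arm flag at 6 or more of 25 in either arm: P(Bin(25, 0.10) ≥ 6) = 3.34% per arm, so 1 − (1 − 0.0334)² = 6.6%.

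| True rate at one dose (other dose 10%) | Pooled flag | Either-arm flag | Gain |
|---|---|---|---|
| 20% | 33% | 40% | 7 points |
| 30% | 70% | 81% | 11 points |
| 40% | 92% | 97% | 5 points |

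A stricter pooled flag of 10 or more of 50 gives 21%, 56% and 85%. Its false-flag rate is only 2.5%, so part of that wider gap comes from the threshold and not from pooling.

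**4. Limits of the split.** Power of the two-sided Fisher test at 5%, with all 25 per arm observed:

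- 0% v 20%: 38%
- 0% v 30%: 81%
- 10% v 30%: 31%
- 10% v 40%: 59%

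If an interim review had 12 per arm (assumed), power for 0% v 20% would be about 7%.

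**The case against.** The case on the other side has several parts.

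**The board is not blinded without exception.** A reader might infer that it can never learn the arms. The Blinding section does not support that, because it allows unblinding for safety reasons. This stands. What remains open is the missing trigger and the missing route to the board.

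**Pooled percentages are not specified.** A reader might infer that the board sees toxicity only as a diluted pooled rate. Neither section says so: symptoms and laboratory results in a 50-person trial could arrive as individual listings. This stands too, although listings without an arm code still cannot show clustering by dose.

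**The board can ask for more.** It includes a statistician, approves the monitoring plans, and may depart from open meetings when privileged data are discussed. Masked tables are not prohibited. They are, however, not provided for, and the named authors cannot produce them.

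**Other safeguards exist.** Toxicity Management sets participant-level actions, related events above Grade 2 go to the IRB within one week, and hematology and chemistries are scheduled at every visit. With no placebo arm, untreated participants do not dilute on-treatment events. These points reduce the consequence, but none of them compares the doses.

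**Blinding the board has a purpose.** The investigator helps write its reports and meetings are open by default, so a blinded board helps keep other roles blinded. That is a fair reason to use masked arms in a closed report instead of open unblinding.

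**Conclusion.** The point holds as a gap in routine reporting. Blinded authors, a blinded board and report contents with no split by arm mean that, as written, the regular reports cannot show whether events concentrate at one dose.

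Its size is modest. Any pooled summary halves the rate of an event confined to one dose, which follows from 1:1 allocation alone. At similar false-flag rates, by-arm review raises detection by about 5 to 11 points, under an assumed 10% background and one-dose rates of 20% to 40%. A reader might infer that the present plan hides a dose-related toxicity and that by-arm tables would reveal it. The figures support neither: a pooled count can still raise a flag, and 25 per arm often cannot separate the doses.

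The change is still worth making, because it is cheap and bears on the only randomised comparison.

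**What to change.** In Blinding and in the Data Safety and Monitoring Plan:

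1. Add a closed board report that tabulates adverse events, laboratory shifts, drug holds and discontinuations by masked arm A/B. Build it from the export the research nurse already makes, and send it to the board's statistician and not to the investigator.
2. State that the board may obtain the A/B key on request, and name the role that releases it.
3. Keep the report prepared by the research assistant and principal investigator pooled, so that their blinding is unaffected.

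The cost is one extra table per twice-yearly meeting, some work for the research nurse, and a rule for custody of the key. There is a small risk that the board guesses which arm is which from the pattern of events.

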- Patients will fill out a dietary, physical activity, and a substance questionnaire.
- Blood will be obtained for markers of inflammation, microbial translocation, oxidative markers, glucose and insulin, chemistries, hematology, lipids and zinc. HIV-1 RNA, and CD4 count will be obtained from the clinical chart as these are part of routine care. Some of the plasma, serum urine and stool will be stored for potential future testing such as additional tests for inflammation, cardiovascular markers, endothelial function markers, oxidative markers. These

blood samples will be batched and the tests will be done at the end of the study and are part of this study.

- For woman of reproductive potential, a urine sample will be taken for a pregnancy test.
- CVD Risk Score
- Whole body DEXA scans will be done at Entry only. Limb fat, lean body mass, trunk fat, total fat, and other measurements will be measured by dual-energy absorptiometry in the anteroposterior view (using the same Hologic scanner for all subjects). An experienced technician will scan each patient using the same machine on all study subjects.
- Resting Energy Expenditure (REE) will be done at Entry and Week 16. REE will be performed in the SIU by the dietician who is experienced with this procedure using the BodyGem and MedGem Measurement Protocol. Patients will be in a fasting state for 8 hours and nicotine free for 1 hour for this test; they will be in a rested state. The total test will take about 30 minutes in a private exam room in the SIU, while the measurement takes 5-10 minutes. A single-use mouthpiece is placed into the flow tube and the device is placed on a flat surface. Subjects will be wearing a one-time use nose clip to force only mouth breathing. The subject breathes normal while the device measures the REE.
- CT scan for Calcium scoring and pericardial fat assessment will be done at Entry only. The use of cardiac CT for CAC scoring to more accurately discriminate CVD risk has grown based upon the observation that CAC occurs almost exclusively in patients with atherosclerotic vascular disease and is not present in normal coronary arteries

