- Endothelial function (EndoPAT): a non-invasive, user-independent technique using the FDA-approved EndoPAT2000 (Itamar Medical Ltd, Israel) provides a reliable and reproducible assessment of endothelial function that predicts atherosclerosis and CVD events. Using modified plethysmographic biosensors, the PAT signal is measured from the fingertip by measuring arterial pulsatile volume changes. A cuff is inflated around the upper arm to obstruct flow and released. The surge of blood flow causes endothelial dependent FMD, manifested as a reactive hyperemia. The EndoPAT® calculate the RHI, the ratio of digital pulse volume during reactive hyperemia and the baseline. In addition to the RHI, we will obtain peripheral Aix, adjusted for HR of 75, which will be compared to central Aix obtained with PWV. We have excellent track record in performing vascular studies, and carefully control for factors that could influence endoPAT; studies are performed at 24 C with the patient resting quietly. Subjects will be fasting, without smoking, caffeine, and exercise for >4 hours. Follow-up studies are completed at the same time of day as the initial study using the same equipment.

-The follow up study visits will be at 4, 10 and 16 weeks (end of study). Fasting is also mandatory for these visits. Below is the detailed events that will occur at these visits.

Week 4 and 10:

- Questionnaires about symptoms or any change in health status
- A short targeted physical exam including weight and blood pressure

- Urine pregnancy test for women
- Assess compliance/safety monitoring
- Blood will be collected for hematology/chemistries. HIV-1 RNA and CD4 count will be obtained from the clinical chart, if available.
- Plasma, serum, urine and stool will be collected and stored for potential future testing

Week 16:

- Targeted physical exam including weight and blood pressure
- Assess compliance/safety monitoring
- Questionnaire about symptoms or any change in health status, substance use and physical activity
- Dietary assessment
- Urine pregnancy test for women
- CVD Risk Score
- EndoPat
- REE
- Blood will be collected for hematology/chemistries, lipids, insulin and zinc
- Plasma, serum, urine and stool will be stored for batch testing (similar to baseline visit) to check for inflammation markers, oxidative markers, and microbial translocation. HIV-1 RNA and CD4 count will be obtained from the clinical chart.

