- For any Grade 4 toxicity (confirmed X 2 values for laboratory abnormalities) regardless of the cause, subjects will be taken off study drugs but will continue to be followed and undergo the evaluations as per schedule of events. Exceptions are asymptomatic elevation of indirect bilirubin in subjects receiving indinavir or atazanavir therapy, asymptomatic elevation of CPK, or elevations in lipid levels.

CRITERIA FOR PERMANENT STUDY DISCONTINUATION

-Request by the subject to withdraw

-At the discretion of the IRB

-Pregnancy or breast-feeding

[figure not shown]
-Request of the primary care physician if s/he thinks the study is no longer in the best interest of the subject.

STATISTICAL CONSIDERATIONS

The primary Aim of this pilot study is to demonstrate that oral dosing of zinc can impact a biological signature in patients with HIV. Biological signatures (hs-CRP, sCD14, sTNF-RI, LBP) will be assessed to determine if giving the natural product (zinc gluconate at 45 mg and 90 mg) to patients with HIV results in a meaningful change in the measure.

Inter-assay variability less than 15% are generally acceptable¹¹. To reduce this variability we will repeat each of these assays twice (run in duplicate) and compute average from the repeated assays performed in the same lab under same conditions conducted by the same technician. Given this set-up, the bioassays will efficiently quantify the biomarkers with less than 6% inter-assay variability which is substantially less than the general acceptable guidelines. Moreover, this inter-assay variability should be equivalent in both sets of measures obtained at baseline and after the Zinc supplementation.

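### The stated assay precision of under 6% does not follow from duplicate runs, and no rule puts a participant's Entry and Week 16 samples in the same run

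*Combined protocol and SAP*

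**What the plan says.** The protocol's STATISTICAL CONSIDERATIONS section opens its case on measurement error with a general benchmark: "Inter-assay variability less than 15% are generally acceptable". It then describes the remedy: "we will repeat each of these assays twice (run in duplicate) and compute average from the repeated assays", with the replicates "performed in the same lab under same conditions conducted by the same technician". From this it concludes: "Given this set-up, the bioassays will efficiently quantify the biomarkers with less than 6% inter-assay variability", and adds that "this inter-assay variability should be equivalent in both sets of measures obtained at baseline and after the Zinc supplementation".

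The next paragraphs rely on that equality. Nuisance variation is taken to be the same before and after, so a shift between the two distributions is read as the effect of treatment. The tests are Kolmogorov-Smirnov, a median test, and an intercept-only regression on post-minus-pre values whose significance is attributed to zinc. Both arms take zinc, and the section itself notes that there is no placebo.

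On timing, the Study Entry procedures say that "blood samples will be batched and the tests will be done at the end of the study", and the Week 16 procedures say that material "will be stored for batch testing (similar to baseline visit".

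**The concern.** Two steps in the argument fail.

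First, averaging duplicates made under the same conditions reduces error within a run. It does not touch an error shared by every well of that run, which is what inter-assay variability describes. The section does not say whether the two replicates sit in one run or two, and it gives no CV for any of the four assays.

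Second, equal spread at two visits says nothing about equal run means. A run that reads low lowers every sample in it. If Week 16 samples fall mainly in such runs, the whole distribution moves left, which is the pattern the plan hopes to see. With no untreated group, nothing in the data would separate that from a zinc effect, and more participants would not help.

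**Working it through.** **Inputs.** From STATISTICAL CONSIDERATIONS: the 15% benchmark, two replicates, the claimed 6%, SDs of 0.35 for log(sCD14) and 0.37 for log(sTNF-RI), mean (SD) of 4.95 (10.45) for hs-CRP and 21.11 (10.91) for LBP, a one-sided 0.10 test, n = 20 per dose and 40 combined, and a target d of 0.20. From STUDY DESIGN: 25 per dose and 50 in all. Assumed, because the documents do not give them: natural logs, pre-post correlation r of 0.5 to 0.8, and the plate layout.

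**Step 1: can 6% be reproduced?** For k independent runs, the CV of the mean is CV/√k.
- Two independent runs: 15/√2 = 10.6%.
- Two replicates in one run, with a fraction f of the variance between runs: 15 × √(f + (1 − f)/2). This is 10.6% at f = 0, 13.0% at f = 0.5 and 15.0% at f = 1.
- Runs needed to go from 15% to 6%: (15/6)² = 6.25, so seven.
- Working back, duplicates give 6% only if the single-determination CV is at most 6 × √2 = 8.5% (independent runs), or between 6.0% (f = 1) and 8.5% (f = 0) within one run.

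No reading of the duplicate scheme gives 6% from 15%, and the documents state no smaller starting CV.

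**Step 2: scale against the target effect.** With r = 0.5 the SD of differences for log(sCD14) is 0.35 × √(2 × 0.5) = 0.35, so d = 0.20 is 0.20 × 0.35 = 0.07 log units, about 7%. The difference between two runs that each have a 6% CV has SD 6 × √2 = 8.5%. A run difference of ordinary size is therefore as large as the effect sought.

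**Step 3: is more than one run likely?** 40 to 50 participants × 2 visits × 2 replicates = 160 to 200 wells per marker. On a 96-well plate (assumed) that is at least two to three plates.

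**Step 4: worst-case error rate.** Suppose that plates are filled by visit and the full 6% is between-run shift. Let SE = SD × √(2(1 − r))/√n and S = 0.06 × √(2/k), with k runs per visit. Under no zinc effect, the probability of rejecting in the direction of benefit is 1 − Φ(1.2816 × SE/√(SE² + S²)), against a nominal 10%.
- Lowest at n = 40-50 (log sTNF-RI, r = 0.5, n = 40, k = 3): SE = 0.0585, S = 0.0490, giving 16.3%.
- Highest at n = 40-50 (log sCD14, r = 0.8, n = 50, k = 1): SE = 0.0313, S = 0.0849, giving 32.9%.
- At n = 20-25 the same corners give 13.5% (SE = 0.0827) and 27.7% (SE = 0.0443).

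**Step 5: sensitivity at n = 40-50, plates still filled by visit.**

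| Case | Rejection under no effect |
|---|---|
| Log markers, all of the 6% variance between runs | 16.3-32.9% |
| Log markers, half of the variance between runs | 13.5-27.7% |
| Log markers, a quarter between runs | 11.9-22.3% |
| LBP, all between runs (SD/mean 0.52) | 13.6-27.0% |
| hs-CRP, all between runs (SD/mean 2.11) | 10.2-12.1% |

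The hs-CRP and LBP rows put the shift on the scale of the mean and use the same normal approximation.

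**Step 6: both samples in one run.** A shift common to the run is in both log values and drops out of the difference, so the test keeps its 10% level.

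**The case against.** The best defence is the batching. Entry samples are held until the end of the study, Week 16 samples are stored for batch testing in the same way, and one laboratory and one technician do the work. That removes the usual reason for visits to be assayed apart. If visits are mixed across runs, a run shift mainly widens the differences and does not imitate zinc. Plate layout may also be set in a laboratory procedure outside this document. All of this stands and lowers the risk. But batching fixes when samples are assayed, not which plate they go on, and filling plates by visit would comply with the text as written.

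A reader might infer that the 6% figure is wrong. The documents do not show that: 15% is a general limit, not this laboratory's CV, and a good assay could already be below 6-8.5%. A reader might also take 16-33% as the trial's expected false-positive rate. It is not. It needs both an assumed layout and an assumed variance split.

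Nor is every analysis exposed. The primary objective also correlates marker change with zinc change, and a shift common to all participants leaves that correlation as it was. hs-CRP, one of the three primary markers, is barely affected. No error rate is derived here for the hypothesis that at least two of four markers shift.

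Finally, if the replicates are in separate runs, averaging does reduce inter-assay variance, so the plan's statement on duplicates needs clarifying, not automatic deletion.

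**Conclusion.** The point holds in a limited form. The precision claim is unsupported by its own reasoning, although it may be true. The appeal to equal variability does not protect the before-after location tests from a run shift. Nothing in the protocol requires paired samples to share a run, balances visits across runs, or adjusts for run.

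The consequence is conditional. The 16-33% (n = 40-50) and 14-28% (n = 20-25) rates are worst-case figures for two of the three primary markers at the plan's own 6%. They fall as the between-run share falls, and the bias largely goes away if visits are mixed across runs. The point is still worth acting on: these tests attribute change to zinc without a control, and once plates have been filled by visit the analysis cannot separate run from treatment.

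**What to change.** Before any batch is assayed:
- Require each participant's Entry and Week 16 aliquots to go on the same plate in the same run, in randomised order, with the technician blind to visit. Coded specimens and the restricted treatment file already go some way towards blinding to arm, but nothing covers visit.
- Replace the 6% statement with the laboratory's documented within-run and between-run CV for each marker.
- State whether duplicates are in one run or in separate runs, and claim a reduction in inter-assay variability only if they are separate.

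This adds no assays, because the samples are already stored for testing at the end. It costs one plate-layout instruction and a corrected paragraph.
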